**History of amendments**

Date: N/A                      Description:  
Version: N/A                      Not applicable – initial version

## LIST OF ABBREVIATIONS

ANSM	National Agency for the Safety of Medicines and Health Products
BOW	Clinical Research Associate
PCBs	Good Clinical Practice
CNIL	National Commission "Information Technology and Freedoms"
CPP	Committee for the Protection of Persons
CRF	Case Report Form
Eff.In	Adverse effect
EI	Adverse event
EIG	Serious Adverse Event
EII	Unexpected adverse reaction
EIGD	Serious adverse reaction to the medical device
EIGID	Unexpected serious adverse reaction from the medical device
IC	Clinical Investigation
MR	Reference Methodology
WOODPECKE R	Clinical Investigation Plan
PTH	Total Hip Replacement

## 1. GENERAL SYNOPSIS OF THE CLINICAL INVESTIGATION

Title	Ambispective study evaluating the clinical outcomes of revision stem SAGITTA EVL R
ID-RCB No.	2022-A02295-38
Protocol version	V1.2
Date	21/12/2022
Promoter	SERF [name]
Principal investigator	[name]
Rationale/Background	This clinical study is being conducted with the aim of collecting data on hip arthroplasty with revision femoral stems from the SAGITTA® EVL-R range of FEMORAL stems manufactured by SERF. In order to reflect current practice, a comprehensive and ongoing series of patients will be included. This study will confirm the performance and safety of the SAGITTA® EVL R range of revision femoral stems within the MDR 2017/745 regulatory framework and in relation to the recommendations of the MEDDEV 2.7.1 guide. Rev 4 (Clinical Evaluation Guide), which provides for the implementation of a systematic procedure for monitoring clinical data in order to verify the claimed performance of medical devices.
Product under investigation	SAGITTA® EVL R revision femoral stems and CLAV distal locking keys. EVL.
Methodology	Post-marketing clinical follow-up study performed according to routine care with additional procedure neither heavy nor invasive, non-interventional ambispective, monocentric, non-comparative, open-label, of an exhaustive and continuous series of patients.
Ethical considerations	The investigation will be conducted in accordance with the investigation protocol, the regulations in force, including the Public Health Code as well as the Medical Devices Regulation 2017/745, the ISO 14155:2020 standard, as well as in accordance with the ethical principles described in the Declaration of Helsinki. The investigation will start as soon as the authorisations from the competent authorities are received in accordance with the typology of the study, category 4.1. As personal data will be collected and analysed during this investigation, SERF complies with the reference methodology MR 001 (declaration 2140288 v 0). The collection of personal data will also be in accordance with GDPR 2016/679. All data and information relating to patients or their participation in this study will be considered confidential and in accordance with applicable laws and regulations will not be made public. The data collected and stored in a pseudonymised format does not allow the identification of a patient through the data collected. Under no circumstances will the names of patients be transmitted or communicated to SERF.

	
Patient consent will be collected by the principal investigator or another surgeon in the department during the on-site follow-up visit.
 
As the EUDAMED database is not yet available, this study will be registered on the public database www.clinicaltrials.gov.

Main objective	
To evaluate the medium-term postoperative survival rate (minimum 4 years postoperatively) of SAGITTA® EVL R rods placed between 2016 and 2018, all causes of revision combined.

Secondary objective(s)	
The secondary objectives of this study are to:
 
 
- Study the survival rate by components and by etiology (revision and revision with reconstruction)
 
- Study the patient's satisfaction with his hip prosthesis
 
- Confirm the safety of these implants by studying any complications observed
 
- Evaluate performance through the clinical scores of HARRIS and forgotten prosthesis score of the revision femoral stems SAGITTA® EVL R.
 

Primary outcome	
The survival rate will be determined according to the Kaplan-Meier curve with the replacement of the femoral implant, all causes combined.

Secondary outcome(s)	
The survival rate by component as well as the survival rate by etiology will be determined according to the Kaplan-Meier all-cause curve.
 
The safety of the implants will be evaluated by the occurrence of adverse events related to the medical device. These elements will be sought by the clinical examination of the practitioner and the radiological examination, carried out as part of routine practice.
 
Patient satisfaction with their hip replacement will be assessed using a satisfaction questionnaire.
 
Implant performance will be assessed through the Harris Clinical Hip Score (HHS) and Forgotten Hip Score (SHO-12).

Description of the study population	
Between January 2016 and December 2018, about 120 patients were operated on with a SAGITTA® EVL R revision femoral stem at the Rouen University Hospital – Charles Nicolle Hospital. All patients with a SAGITTA® EVL R revision femoral stem will be seen again at a medium-term postoperative follow-up visit (minimum 4 years postoperatively). During this follow-up, they will be offered to participate in this clinical investigation.

Criteria for Inclusion of Subjects	
 
- Patient of legal age on the date of surgery,
 
- Patient implanted with a SAGITTA® EVL R revision femoral stem as part of its indications between 01/01/2016 and 31/12/2018,
 
- Patient with a health insurance scheme
 

Criteria for non-inclusion of subjects	
 
- Patient who has not expressed consent to the collection of his/her data and participation in the study,
 
- Patient unable to understand the surgeon's instructions or perform postoperative follow-up.
 

	

- Patient with a contraindication to the use of the SAGITTA® EVL R revision femoral stem

- Patient implanted with a SAGITTA® EVL R revision femoral stem outside of their indication

Number of Subjects	As the study is descriptive, there is no calculation of the number of subjects needed according to a hypothesis. All patients operated on at the Rouen University Hospital – Charles Nicolle Hospital and with a SAGITTA® EVL R femoral stem will be included. This represents about 120 patients.
Treatment(s)/procedure(s) related to the study	
Prospective part:
 
According to the centre's practice, as part of the systematic follow-up of hip replacement replacements, a clinical examination will be carried out with an assessment of any complications and patient satisfaction. Only a quality of life questionnaire (SHO-12) and the HHS score will be required by this HF in addition to the standard care practiced in systematic follow-up in this center. These questionnaires will be completed jointly by the patients and the surgeon (additional procedure that is neither heavy nor invasive).
 
Routine radiological evaluation will be performed. It allows the evaluation of osseointegration and bone reconstruction to document possible complications.
 
The collection of its data will be carried out in a paper case report form (CRF).
 
Retrospective part:
 
In accordance with the patient's agreement, retrospective data will be collected using the patient's medical record and will be collected in the CRF.
 
No additional examination to current practice will be carried out as part of this investigation.

Total duration of the study	The prospective portion of the study will last approximately 5 months depending on patient availability. The duration of each patient's participation in this study is limited to this single consultation. Retrospective data collection will be carried out simultaneously. This is a total duration of the study of 5 months.
Study timeline	The prospective part will begin as soon as regulatory approvals are obtained, scheduled for January 2023 and will be completed in May 2023. The retrospective part will be conducted after the patient consent has been collected. Study closure and report writing: July 2023
Statistical analysis	A statistical analysis will be carried out at the end of the study. This analysis will be carried out by SERF. A descriptive analysis will be done based on the data collected during the study. A follow-up of the events that occurred will be carried out, as well as an analysis of the survival rate according to Kaplan Meier.

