#### **Functional Clinical Scores and Ratings**

- *Harris Hip Score*:

The Harris score (HHS) is one of the main functional clinical scores used after hip replacement surgery and evaluates 3 "items" relating to the diseased or operated hip:

- Pain (44 points)
- Function (47 points)
- Mobility (9 points)

For a maximum total score of 100 (minimum score:0), the HHS results will be categorized as follows:

 Harris WH. Traumatic arthritis of the hip after dislocation and acetabular fractures: treatment by mold arthroplasty. An end-result study using a new method of result evaluation. *J Bone Joint Surg Am.* 1969; 51: 737–55.

HHS	
Excellent	90-100
Good	80-89
Correct	70-79
Bad	< 70

The HHS fill grid is available in **Appendix 5**.

- *Forgotten Hip Score (FJS-12):*

The Forgotten Hip Score (SHO-12) is the French version of the FJS-12 (*Forgotten Joint Score*). The objective of this self-questionnaire is to estimate the degree of neglect of the hip and knee prosthesis through 12 questions.

Each item has 5 levels of response:      Never: 0 points

Almost never: 1 point  
Rarely: 2 points  
Sometimes: 3 points  
Often: 4 points

The sum of the items is divided by the number of items and multiplied by 25 to obtain a score out of 100.

The OHSS Fill Grid is available in **Appendix 6**.

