## D. PROCEDURES

### i. DESCRIPTION OF ANY HF-RELATED PROCEDURES TO WHICH SUBJECTS ARE SUBJECTED (INCLUDING DEVIATIONS FROM STANDARD CARE)

Only an additional procedure that is neither heavy nor invasive is required when participating in this HF compared to the standard care provided as part of the systematic follow-up during hip replacement revision surgery in the investigation center in question. Namely, a quality of life questionnaire (SHO-12 forgotten hip score) and a functional score (HHS Harris Hip Score) are requested in addition. These can be completed in part by the patient or collected by the investigator.

As far as the retrospective part is concerned, all the necessary data will be collected directly from the patients' medical records, the subjects having already undergone the following visits: preoperative visit, intervention, immediate postoperative follow-up. Depending on the date of the operation, one or more intermediate postoperative follow-ups may have been performed. Data on these interim follow-ups will not be collected. Only relevant data in terms of serious adverse events will be collected for these interim follow-ups.

For the prospective part, which concerns only the medium-term postoperative follow-up (minimum 4 years) taking place after the inclusion of patients in the study, the procedures to which the subjects participating in HF will be subjected are listed and briefly described below. These procedures are the same as those performed as part of the systematic follow-up of a hip replacement in the investigation center in question. At the end of the investigation, the subjects continue to be monitored according to the habits of the center.

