### **Follow-up visits**

The follow-up visit will take place as follows: the subject meets the investigator for the systematic clinical examination as carried out in the investigation center, with a search for signs indicating the possible presence of a complication in the operated hip and the evaluation of the patient's satisfaction. The pain experienced by the subject will be reported via the HHS score. HHS and SHO-12 functional scores are collected by the investigator via the appropriate questionnaires submitted to the patient (see Appendices 5 and 6 and section 6.A.iii). Bone reconstruction and osseointegration are evaluated on the X-ray performed prior to the follow-up visit to document a complication. If a revision, removal or change of implant is necessary or in the case of the detection of a complication, the investigator records this in the patient's file.

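### The protocol does not settle whether patients answer the SHO-12 and the satisfaction item alone or with a surgeon, so mode of completion may vary and shift two secondary outcomes

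*Protocol*

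**What the plan says.** **SHO-12.** Four places in the protocol bear on how it is completed.

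- Section 6.A.iii, on functional scores, defines the instrument: "The objective of this self-questionnaire is to estimate the degree of neglect of the hip and knee prosthesis through 12 questions".
- The synopsis (section 1, study procedures) names the SHO-12 and the Harris Hip Score (HHS) as the two additions to standard care and continues: "These questionnaires will be completed jointly by the patients and the surgeon".
- Section 6.D.i names the same two instruments and says: "These can be completed in part by the patient or collected by the investigator".
- The follow-up visit text in section 6.D.i says: "HHS and SHO-12 functional scores are collected by the investigator via the appropriate questionnaires submitted to the patient".

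**Satisfaction.** Section 6.A.iii specifies a five-level Likert scale. The synopsis states that patient satisfaction "with their hip replacement will be assessed using a satisfaction questionnaire". It also places the assessment inside the consultation: "a clinical examination will be carried out with an assessment of any complications and patient satisfaction". The follow-up visit text begins "the subject meets the investigator for the systematic clinical examination as carried out in the investigation center" and lists "the evaluation of the patient's satisfaction" among the contents of that meeting. No section names the person who marks the scale.

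**Who is present.** Section 2.G.i reserves follow-up to an orthopaedic surgeon. The synopsis has consent taken at the visit by the principal investigator or another surgeon of the department. The study has one centre.

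**The concern.** The SHO-12 and the satisfaction item are the only outcomes that consist purely of the patient's own report. If a surgeon from the department that implanted the stem helps with the answers, patients may answer more kindly than they would alone. If some patients are helped and others are not, part of the spread between patients reflects the mode rather than the hip.

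A controlled study would lose much of such a shift in the comparison. This one has no comparator (section 6.B), and the schedule in section 6.A.iv excludes the SHO-12 from the preoperative data, so there is no within-patient change to fall back on either. The level at follow-up is the result. Because each patient is seen once, the mode cannot be reconstructed later unless it is written down at the visit.

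**Working it through.** The protocol gives no figure for a mode effect, so there is none to reproduce. The check is a comparison of texts, followed by arithmetic for scale only.

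**Step 1: does any passage fix the mode of the SHO-12?**

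| Place in the protocol | Mode as worded | Patient alone? |
|---|---|---|
| 6.A.iii, functional scores | Self-questionnaire | Implied |
| Synopsis, study procedures | Patient and surgeon jointly, both instruments | No |
| 6.D.i, opening paragraph | Partly by the patient, or collected by the investigator, both instruments | Not required |
| 6.D.i, follow-up visits | Collected by the investigator on forms given to the patient | Possible, not required |

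The first two rows do not agree for the SHO-12. The third allows alternatives. The fourth fits the first but does not exclude the second. No section requires the patient to answer alone or asks for the mode to be recorded.

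**Step 2: satisfaction.** Both descriptions of the visit put it within the surgeon's consultation. The instrument is called a questionnaire, which suggests the patient may mark it, but this is not stated. The mode is open rather than contradictory.

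**Step 3: is the issue already acknowledged?** Section 6.A.ii mentions the quality of retrospective data. Section 6.D.iii mentions losses, deaths, retrospective data and confounding. Section 7.I.i mentions the lack of a comparator, randomisation and blinding. None mentions assisted answers.

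**Step 4: scale of the SHO-12.** Section 6.A.iii divides the sum of the items by the number of items and multiplies by 25. With 12 items, a shift of one response level on k items moves the score by k × 25/12:

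- k = 1: 25/12 = 2.1 points
- k = 3: 75/12 = 6.25 points
- k = 12: 300/12 = 25 points, the arithmetical ceiling for a one-level shift

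As that rule is printed, a more favourable answer lowers the score.

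**Step 5: scale of satisfaction.** If a fraction f of patients moves from the neutral level to the level above it, the satisfied share rises by f. Assuming f between 5% and 15% gives 5 to 15 percentage points. This only restates the assumption; f = 0 is equally consistent with the documents.

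**Step 6: would the planned intervals show it?** The intervals in section 7.C.i are built from p and n, or from the standard deviation and n. They reflect sampling error. A common shift would move the estimate and leave the interval centred on the shifted value.

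**The case against.** The strongest reply is that the wording is loose rather than contradictory. The synopsis and section 6.D.i describe the two instruments as a pair, so joint completion may mean that the patient answers the SHO-12 and the surgeon does the examination items of the HHS. Collecting a form is not the same as completing it. The follow-up visit text has the questionnaires given to the patient. The document also reads as a translation, so fine differences between verbs deserve little weight. Much of this stands: a reader might infer three firmly established and incompatible modes, and the text does not go that far. What remains is that one sentence is applied to both instruments in each place and the split is never made.

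A reader might also infer that the implanting surgeon personally puts the satisfaction question to the patient and records the answer. The protocol does not say so. It places the item in the surgeon's visit and is silent on who marks it. Nor does it say that the assessor is the surgeon who operated, only that this is the same department.

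A third objection concerns the remedy. Having the forms filled in before the patient sees the surgeon looks natural, but the SHO-12 is added by the study, and the study summary in section 6.D.i puts information and consent before data acquisition at that visit. Completion before consent would conflict with this. The objection is right, and the change has to respect that order.

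Finally, the HHS would still be collected by the surgeon. Pain (44) and function (47) make up 44 + 47 = 91 of its 100 points and rest largely on what the patient says. That is fair: the remedy does not remove the same possibility there.

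**Conclusion.** The point holds as a defect in how data collection is specified. The protocol calls the SHO-12 a self-questionnaire, elsewhere permits surgeon-assisted completion, and leaves the completion of the satisfaction item open. Followed as written, it allows the mode to differ between patients without a record.

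A reader might go further and conclude that the results will be biased in favour of the implant. The documents do not support that. They give neither direction nor size, the effect may be zero, and the figures of 2.1, 6.25 and 25 points only translate response levels into score points. That any shift would be favourable is an inference from the setting.

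The reach is limited to secondary outcomes that are descriptive, with no hypothesis, test or pass/fail criterion (sections 5.D, 7.G and 7.I.iv). The survival analysis is untouched. The correction is still worth making before the first visit, because it is cheap and the mode cannot be recovered afterwards.

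**What to change.** Bring the synopsis and both parts of section 6.D.i into line with the description in section 6.A.iii:

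- After consent at the visit, the patient completes the SHO-12 and the five-level satisfaction item alone, on paper, before or apart from the surgeon's examination.
- The surgeon completes the HHS.
- A CRF tick box records whether the patient was helped with either form, so that assisted answers can be listed separately.
- Add to the bias section that the HHS pain and function answers are collected by a surgeon of the implanting department, as a limitation.

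The cost is a small change in the order of the visit, including for satisfaction, which the centre already assesses routinely, and one field in the CRF. No extra visit, staff or item is needed. The downside is a few more blank items from patients who would otherwise have been helped. Allowing help, and recording it, limits that loss.

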## 2. IDENTIFICATION AND DESCRIPTION OF THE DEVICE UNDER INVESTIGATION

### A. DESCRIPTION AND INTENDED USE

The devices under investigation in this clinical investigation (CI) are the SAGITTA® EVL R revision rods, the fixation of which can be completed by the use of two CLAV distal locking keys. EVL.

The SAGITTA® EVL R femoral stem range, in combination with the prosthetic heads and two optional distal locking keys, is suitable for most femoral revisions of total hip prosthesis (THP) with bone defect (Paprosky type I to III and SOFCOT stage II to IV) in order to reduce pain and restore mobility of the hip joint.

### C. DEVICE UNDER INVESTIGATION

Revision femoral stems **SAGITTA® EVL R** (Figure 1) are long, uncemented stems. They are made of forged TA6V alloy (ISO 5832-3 compliant). They have a hydroxyapatite coating (compliant with 13779-2) along the entire implantable length of the stem.

The curved distal part takes up the anatomical arch. The cervico-diaphyseal angle is 130°. The 11/13 assembly cone has an average angle of 4°.

The SAGITTA® EVL R rod range consists of 14 rods on the right side and 14 rods on the left side, with 3 different rod lengths for each side (180 mm, 250 mm or 325 mm).

The attachment of the revision rod can be completed with 2 transcortical locking keys made of titanium (Figure 1) TA6V (ISO 5832-3). With a diameter of 4.5 mm, they are available in 9 lengths: 25; 30 ; 35 ; 40 ; 45 ; 50 ; 55 ; 60 and 65 mm.

Figure 1 - At the top, a revision femoral stem SAGITTA® EVL R; at the bottom, a distal locking key CLAV. EVL

The rod references (

Table 1) and keys (Table 2) used in this CI are set out below:

Table 1 – Lengths, sizes, diameters, labels and references of the rods SAGITTA® EVL R

Length	Waist	∅ (mm)	Right Side		Left side	
			Wording	Reference	Wording	Reference
180 mm	2	12	SAGIT. EVL R 2-180 D	RM10450500	SAGIT. EVL R 2-180 G	RM10450520
	3	13	SAGIT. EVL R 3-180 D	RM10450501	SAGIT. EVL R 3-180 G	RM10450521
	4	14	SAGIT. EVL R 4-180 D	RM10450502	SAGIT. EVL R 4-180 G	RM10450522
	5	15	SAGIT. EVL R 5-180 D	RM10450503	SAGIT. EVL R 5-180 G	RM10450523
	6	16	SAGIT. EVL R 6-180 D	RM10450504	SAGIT. EVL R 6-180 G	RM10450524
250 mm	2	12	SAGIT. EVL R 2-250 D	RM10450505	SAGIT. EVL R 2-250 G	RM10450525
	3	13	SAGIT. EVL R 3-250 D	RM10450506	SAGIT. EVL R 3-250 G	RM10450526
	4	14	SAGIT. EVL R 4-250 D	RM10450507	SAGIT. EVL R 4-250 G	RM10450527
	5	15	SAGIT. EVL R 5-250 D	RM10450508	SAGIT. EVL R 5-250 G	RM10450528
	6	16	SAGIT. EVL R 6-250 D	RM10450509	SAGIT. EVL R 6-250 G	RM10450529
325 mm	3	13	SAGIT. EVL R 3-325 D	RM10450510	SAGIT. EVL R 3-325 G	RM10450530
	4	14	SAGIT. EVL R 4-325 D	RM10450511	SAGIT. EVL R 4-325 G	RM10450531
	5	15	SAGIT. EVL R 5-325 D	RM10450512	SAGIT. EVL R 5-325 G	RM10450532
	6	16	SAGIT. EVL R 6-325 D	RM10450513	SAGIT. EVL R 6-325 G	RM10450533

*Table 2 - Lengths, diameter, labels and references of the optional CLAV distal locking keys. EVL*

Length	∅	Wording	Reference
25 mm	4.5 mm	CLAV. EVL 25	RM69020020
30 mm		CLAV. EVL 30	RM69020021
35 mm		CLAV. EVL 35	RM69020022
40 mm		CLAV. EVL 40	RM69020023
45 mm		CLAV. EVL 45	RM69020024
50 mm		CLAV. EVL 50	RM69020025
55 mm		CLAV. EVL 55	RM69020026
60 mm		CLAV. EVL 60	RM69020027
65 mm		CLAV. EVL 65	RM69020028

The stems SAGITTA® EVL R as well as the CLAV keys. EVLs are long-term implantable medical devices that are invasive, sterile, non-active and do not contain drugs or biologically active substances (tissues of human or animal origin, or their derivatives), their regulatory description is available in the Table 3.

*Table 3 - Regulatory description of products under investigation*

Device	Class	Code GMDN	CE marking
SAGITTA EVL R	III	38155 – Press-fit femoral stem prosthesis	2003
CLAV. EVL	IIb	46646 – Orthopaedic bone screw, non-bioabsorbable, sterile	2003

**Note:** for the rest of the CI, under the terms "SAGITTA® EVL R" or "rods" will be included both the SAGITTA® EVL R revision femoral stems and the optional CLAV distal locking keys. EVL, unless specifically specified. The keys can only be used with the rods, so they share the same intended use (target population, indications, etc.) as the latter.

